#### 3.4.2 Exploratory Efficacy Endpoints

The exploratory efficacy endpoints include the following:

- Change in Skindex-29 scores (symptoms domain, emotions domain, functioning domain, overall score) from baseline to Weeks 1, 2, 8, 12, 26, 39, 52, 78, 104, 130, and 156
- Change in patient global assessment (PGA) from baseline to Weeks 1, 2, 8, 12, 26, 39, 52, 78, 104, 130, and 156
- Change in physician global assessment (PhGA) from baseline to Weeks 1, 2, 8, 12, 26, 39, 52, 78, 104, 130, and 156
- Number of participants on prednisone dose 0 mg/day at Weeks 12, 26, 39, 52, 78, 104, 130, and 156
- Number of participants requiring an increase in prednisone dose relative to last recorded prednisone dose at any time prior to Weeks 12, 26, 39, 52, 78, 104, 130, and 156

#### 3.4.3 Exploratory Mechanistic Endpoints

The exploratory mechanistic endpoints include the following:

- Determine the relative frequency of adoptively transferred Tregs in blood and skin by quantifying transferred deuterium-labeled Tregs in peripheral blood and skin from Week 1 to 12. In addition, TCR sequencing may be performed on sorted Tregs from either skin or blood.
- Perform whole transcriptome RNA sequencing to determine the effects of PolyTreg infusion on inflammatory and immunoregulatory pathways in the target tissue (skin)
- Quantify inflammatory cell subsets and immunologic biomarkers in blood and skin, including changes in lymphocyte subsets, cytokine profile, and autoantibody production
- Changes in disease specific and immunologic biomarkers in peripheral blood including lymphocyte subsets, cytokine profiles, polyclonal and antigen-specific Treg function (flow cytometry with MHC II-tetramer staining), and autoantibody production from baseline to Weeks 1, 2, 8, and 12

- Changes in disease specific and immunologic biomarkers in skin including lymphocyte subsets, polyclonal and antigen-specific Treg function (flow cytometry with MHC II-tetramer staining), and cytokine profiles from baseline to Weeks 1 and 12

## 4 SELECTION OF SUBJECTS

Subjects with pemphigus must grant written informed consent prior to the subject undergoing any study-related procedure, including screening tests and medication adjustments, when applicable.

### 4.1 Inclusion Criteria

Subjects who meet all of the following criteria are eligible for enrollment into the study:

1. Ability to provide informed consent
2. Age 18-75 years at Screening Visit
3. Diagnosis of PV or PF, defined by H&E and direct immunofluorescence staining of skin biopsy at any time prior to enrollment
4. Pemphigus treated with systemic corticosteroids within the 2 years prior to screening (historic or current) or treated with rituximab at least 12 months prior.
5. Presence of:
  - a. anti-Dsg3 antibodies (>20.0 U/ml) at screening visit consistent with diagnosis of pemphigus vulgaris, or
  - b. anti-Dsg1 antibodies (>20.0 U/ml) at screening visit consistent with diagnosis of pemphigus foliaceus
6. Active PV or PF as defined by PDAI overall activity score 3-10 at screening visit, and PDAI overall activity score 1-12 at baseline visit
7. Positive test for EBV antibody
8. Adequate venous access to support draw of 400 ml whole blood and infusion of investigational therapy
9. An absolute Treg count of  $\geq 42$  cells/ $\mu$ L within 6 weeks prior to whole blood collection at Week -2

### 4.2 Exclusion Criteria

Subjects who meet any of the following criteria are ineligible to participate in the study:

1. Initiation of systemic corticosteroid therapy, prednisone dose > 25 mg/d (or equivalent) or change in prednisone dose within 4 weeks prior to screening
2. Addition of a new medication, or change in the dose of any background medication used to treat any aspect of pemphigus within the timeframes listed below. Specifically:
  - a. methotrexate, mycophenolate mofetil, mycophenolic acid, azathioprine, cyclosporine or dapsone within the 6 weeks prior to screening or in the time between screening and study drug infusion

- b. IVIG within 12 weeks prior to screening or in the time between screening and study drug infusion (subjects on IVIG must be on stable dose for at least 12 weeks prior to screening)
    - c. treatment with cyclophosphamide within 12 weeks prior to screening or in the time between screening and study drug infusion
3. Doses of background medications at screening:
  - a. methotrexate > 25 mg/week
  - b. mycophenolate mofetil > 3000 mg/d
  - c. mycophenolic acid > 1080 mg/bid
  - d. azathioprine > 200 mg/d
  - e. cyclosporine > 2 mg/kg/d
  - f. dapsone >250 mg/d
  - g. IVIG > 4mg/kg IV monthly
4. Use of rituximab within the 12 months prior to screening
5. Change in dosing frequency, concentration, or applied surface area of topical steroids and/or topical calcineurin inhibitors within 2 weeks prior to screening
6. Paraneoplastic pemphigus
7. Pemphigus erythematosus
8. Pemphigus vegetans
9. IgA pemphigus
10. Drug-induced pemphigus
11. Blood donation within 10 weeks prior to baseline visit (Day 0)
12. Hemoglobin < 10 g/dl
13. White blood cell (WBC) count < 3,000/ mm^3 (equivalent to < 3 x10^9/L)
14. Absolute lymphocyte count < 800/mm^3 (equivalent to < 0.8 x10^9/L)
15. Absolute neutrophil count < 1,500/mm^3 (equivalent to < 1.5 x10^9/L)
16. Platelets < 100,000/mm^3 (equivalent to < 100 x 10^9/L)
17. Liver function test (aspartate aminotransferase [AST], alanine aminotransferase [ALT], or alkaline phosphatase [ALK]) results that are ≥ 2 times the upper limit of normal (ULN)
18. Direct bilirubin > ULN
19. End stage renal disease (estimated glomerular filtration rate [eGFR] < 20 ml/min/1.73m^2 using the CKD-EPI equation [59])
20. At or within three months of screening:
  - a. positive QuantiFERON®-TB Gold test or positive purified protein derivative tuberculin skin test (PPD) (>5mm induration, regardless of Bacille Calmette Guerin [BCG] vaccine administration) unless completion of treatment has been documented for active TB
  - b. an indeterminate QuantiFERON®-TB Gold test unless followed by a subsequent negative PPD or negative QuantiFERON®-TB Gold test as well

as a consultation with and clearance by local infectious disease (ID) department

21. Recent or ongoing active bacterial, viral, fungal, or opportunistic infections requiring systemic anti-infective therapy
22. Evidence of current or prior infection with human immunodeficiency virus (HIV), hepatitis B (as assessed by HBsAg and anti-HBc Ab) or hepatitis C (as assessed by anti-HCV Ab)
23. Detectable circulating EBV or CMV genomes or active infection
24. Chronic infection that is currently being treated with suppressive anti-infective therapy, including but not limited to tuberculosis, pneumocystis, CMV, herpes zoster, and atypical mycobacteria, with the exception of historical orolabial or localized cutaneous herpes simplex infections treated with suppressive anti-viral therapy
25. Receipt of a live-attenuated vaccine within 12 months prior to screening
26. Concomitant malignancies or a history of malignancy, with the exception of completely treated basal cell carcinoma of the skin
27. Pregnancy
28. Lactating or breastfeeding
29. Unwilling or unable to use reliable method(s) of contraception (as described in Section 5.6.3, *Reproductive Risks*)
  - a. For females of child-bearing potential, from four weeks prior to Day 0 through 1 year after Treg dosing
  - b. For males, from the day of Treg infusion (baseline visit) to three months after Treg infusion
30. Use of an investigational therapeutic medication, or other biologic medications except rituximab, within the past 90 days, or 5 half-lives prior to screening, whichever is greater
31. Concomitant medical condition that places the subject at risk by participating in this study, including but not limited to:
  - a. another severe, systemic autoimmune disease or condition (besides pemphigus) requiring systemic immunosuppressive therapy (e.g., rheumatoid arthritis, SLE, systemic sclerosis, primary Sjorgen's syndrome, primary vasculitis, psoriasis, multiple sclerosis, ankylosing spondylitis, and inflammatory bowel disease), or
  - b. severe, progressive, or poorly controlled renal, hepatic, hematological, gastrointestinal, pulmonary, cardiac, or neurological disease, or
  - c. history of significant infection or recurrent infection that, in the investigator's opinion, places the subject at risk by participating in this study, or
  - d. any other concomitant medical condition that, in the investigator's opinion, places the subject at risk by participating in this study
32. Comorbidities requiring glucocorticoid therapy, including those which have required three or more courses of systemic glucocorticoids within the previous 12 months
33. Current or history within the past year of substance abuse
34. Inability to comply with study and follow-up procedures

#### 4.2.1 Co-enrollment Guidelines

Subject may be in observational registries or cohorts as long as the combined blood draw totals do not exceed the limits of the local institutional review boards and objectives do not confound the current study.

## 5 DESCRIPTION OF STUDY PRODUCT

### 5.1.1 Product Description

The name of the drug product is: *Ex Vivo* Expanded Autologous CD4+CD127lo/-CD25+ Polyclonal Regulatory T Cells (PolyTregs). PolyTregs are cells that have been collected from the donor by phlebotomy, purified by Ficoll density gradient, and subsequently selected for the target CD4+CD127lo/-CD25+ T cell subset by FACS, using three monoclonal antibodies specific for the cell surface antigens CD4, CD127, and CD25. The isolated cells are then expanded using anti-CD3/anti-CD28-coated magnetic microbeads in cell culture medium containing deuterated glucose ([6,6-H2]-Glucose) (see Section 6.5.1 for more information on deuterium labeling) for a total of 14 days before harvesting. Following expansion, anti-CD3/anti-CD28 beads are removed via a magnetic separation system, and cell cultures are combined, washed and adjusted to desired concentration.

The CD4+CD127lo/-CD25+ PolyTreg product is a sterile cell suspension of fresh, non-cryopreserved cells in a mixture of 75% FDA approved infusion solution conforming to USP standards (49.02% (v/v) Plasma-Lyte A, 49.02% (v/v), Dextrose 5% with 0.45% NaCl, and 1.96% (v/v)) and 25% Human Serum Albumin (HSA). The final product is administered via IV over a 10-30 minute period by gravity.

The product will be manufactured at UCSF Human Islet and Cellular Transplantation Facility (HICTF) and GMP Facility (San Francisco, CA).

#### **Ex Vivo Expansion of Human Autologous PolyTregs**

Study subjects will provide up to a target of 400 ml of whole blood via phlebotomy to obtain an adequate number of cells for product manufacture. Whole blood will be transported to the manufacturing facility for processing. Previous studies [60] have shown that this process can be conducted successfully using cells obtained locally or at other sites that ship to UCSF.

PBMC will be isolated by Ficoll gradient density centrifugation. The pooled lymphocytes will be stained with clinical-grade fluorescently conjugated antibodies and sorted for CD4+CD127lo/-CD25+ T cells using a commercial cell sorter. Tregs will be expanded per standard operating procedures adapted from optimized methods previously described [23]. This method uses co-stimulation of the Tregs with anti-CD3 and anti-CD28 immobilized on magnetic beads. Enriched Tregs will be cultured in growth medium containing human serum and deuterated glucose and stimulated to proliferate over a 14-day period in the presence of IL-2 and above-mentioned beads. Cultures will be maintained in sterile culture vessels or bags in a humidified 37°C 5% CO2 incubator throughout the culture period. Cells will be counted every 2 to 3 days and transferred to vessels of increasing size to maintain appropriate cell density as cells proliferate, and fresh medium and IL-2 will be added at each cell passage. Cells will be restimulated with additional anti-CD3/anti-CD28 beads at day 9 of the culture period. Cultures will be tested for presence of bacteria, fungus, mycoplasma, and

endotoxin at several interim time points during the expansion period. Following expansion, the beads will be removed via a magnetic separation and the cells will be concentrated, consolidated, and resuspended in sterile infusion solution at the required concentration.

The investigational product will be quarantine refrigerated and will be released with an Interim CoA. The final CoA will be provided once all sterility test results are available.

Studies will be run on the final product for infusion to identify the dominant Treg clones.

Results from bacterial and fungal testing of the final product will be available 14 days and 4 weeks post-infusion, respectively.

### 5.1.2 Packaging and Labeling of Study Product

The Tregs product will be manufactured for subjects at UCSF and the remote sites. It will be shipped to the remote clinical sites via next-day service using validated conditions and containers. Qualified staff at the remote sites will receive the PolyTregs, verify the recorded shipment temperatures were maintained within the validated range, and assess viability and recovery of the product according to UCSF established SOPs.

PolyTregs will be supplied fresh, in sterile 150 ml infusion bags. Label information will be consistent with applicable regulations. All information on the completed label will be verified as accurate by at least two individuals prior to transport to the infusion site.

### 5.1.3 Storage and Handling of Study Product

The Treg product is delivered to the bedside in a temperature controlled container (2-10°C) and is removed from the container just before being administered to the subject. The infusion of the product must occur before expiration time as indicated on the CoA.

Unused product will be disposed in accordance with established standard operating procedures or placed in archive if authorized by the subjects on the informed consent form.

## 5.2 Dosage Regimen

A single infusion of  $1.0 \times 10^8$  or  $2.5 \times 10^8$  PolyTregs will be administered.

## 5.3 Administration of Study Product

### 5.3.1 Preparation for Administration

On the day of scheduled infusion, blood chemistries, a complete blood count (CBC) with differential blood count, and a pregnancy test (for women of childbearing potential) will be obtained locally and reviewed prior to infusion of the PolyTregs. A pre-infusion checklist (see Section 15.6, *Pre-Infusion Required Checklist*) will be used to review relevant clinical and laboratory data prior to infusion. Cell infusion may be held based on the pre-infusion checklist at the discretion of the site investigator. A history of any recent illness or fever will be obtained. The subject should be both asymptomatic and the illness should be resolved before infusion. See Section 5.3.4 for additional criteria for withholding study treatment.

Subjects will be pre-medicated with acetaminophen 650 mg by mouth and diphenhydramine hydrochloride 25-50 mg by mouth or intravenous (IV), approximately 30 minutes prior to the infusion of Tregs. These medications may be repeated every six hours as needed. A course of non-steroidal anti-inflammatory (NSAID) medication may be prescribed if the patient exhibits a fever not relieved by acetaminophen. Patients will not receive systemic glucocorticoids higher than their usual dose such as hydrocortisone, prednisone, prednisolone (Solu-Medrol) or dexamethasone (Decadron).

Prior to administration, the identity of the subject and of the lot are verified by two individuals at the clinical site.

### 5.3.2 Administration

After double verification of cell therapy product and recipient identification, the cells will be infused via a peripheral IV line with an 18-gauge needle primed with saline per established standard operating procedures. All doses will be administered by peripheral IV line via gravity in approximately 20 to 30 minutes. Following administration of the PolyTregs, the product bag, tubing, and peripheral IV line will be flushed with normal saline to ensure complete dose is infused.

Vital signs (temperature, respiratory rate, pulse, and blood pressure) will be taken immediately prior, midway, and at completion of the infusion, and then every 15 minutes (+/- 3 minutes) for at least one hour and longer at this interval as indicated to confirm vital signs are stable. From then on, vital signs will be monitored approximately every hour until four hours post-infusion and approximately every four hours thereafter until discharge.

The IV catheter will be maintained after the infusion until discharge and the subject will remain in the clinical research unit for 24 hours. The subject will be contacted by telephone daily for the next 2 days to assess condition and AEs.

If a study subject experiences symptoms suggestive of an infusion reaction during administration, study treatment will be slowed or temporarily stopped. The subject will be monitored until symptoms resolve. If symptoms can be resolved with acetaminophen, diphenhydramine, or other medication (other than glucocorticoids) at the discretion of the investigator, the infusion may be restarted at the original rate. (Section 5.5.1 *Criteria for Interruption of Study Treatment*)

Emergency medical equipment (i.e., emergency crash code cart) will be made available for the infusion in case the subject has an allergic response, severe hypotensive crisis, or any other reaction to the infusion.

### 5.3.3 Action Plan for Post Release Positive Sterility Results

The results of aerobic bacterial culture, anaerobic bacterial culture, and fungal culture on the final product will not be available prior to product release. In the event of a post-release bacterial or fungal positive result, the finding will be reported to the clinical investigator, institutional review board (IRB), and FDA and a temporary suspension in enrollment will be in effect until a cause is identified and remedied, if required (see Section 5.5.4, *Safety Stopping Guidance*).

The clinical team (site PI[s]) will consult with local infectious disease specialists, and anti-microbial therapy will be considered for the subject as deemed appropriate by the clinical team. The cause of the sterility failure will be investigated and necessary corrective actions will be implemented. The sterility failure, results of investigation of the cause, and corrective actions will be reported to the FDA within 30 calendar days of the receipt of the positive culture test result.

#### 5.3.4 Criteria for Withholding Study Treatment

Infusion of study product is to be withheld if the subject is experiencing any of the following on the day of infusion:

- Fever > 38.0°C
- Acute Diarrhea and/or Vomiting
- Other signs/symptoms of an intercurrent NCI-CTCAE Grade 2 or higher infection.
- Significant pemphigus relapse/flare (PDAI >12)
- Other elements precluding infusion as per the study pre-infusion checklist (see Section 15.6, *Pre-Infusion Required Checklist*)
- Other comorbid conditions which in the opinion of the investigator would pose risk to the subject with administration of the study product

#### 5.4 Repeat Screening When Infusion is Not Given as Scheduled

If the participant completes the Week -2 visit (400ml blood donation) and does not receive the infusion on Day 0 as scheduled, the participant may be eligible to return to repeat screening no sooner than 8 weeks following the preceding blood donation. If the repeat Week -2 visit (blood donation) is scheduled:

- Less than or equal to 12 weeks after initial blood donation, only Hematology and whole blood quantitative PCR for EBV/CMV viral load must be repeated, with other screening tests repeated as clinically indicated
- Greater than 12 weeks after initial blood donation, all screening assessments must be repeated

#### 5.5 Treatment Interruption and Discontinuation

Treatment will consist of a single infusion of *ex vivo* expanded PolyTregs. Once a PolyTreg infusion has concluded, the treatment phase of the protocol is complete. Thus, the question of subsequent withdrawal from treatment will not arise. Therefore, all subjects who undergo an infusion will continue per protocol unless they choose to withdraw (see Section 5.5.3, *Subject Withdrawal from the Study*).

##### 5.5.1 Criteria for Interruption of Study Treatment

If a study subject experiences symptoms suggestive of an infusion reaction during administration, study treatment will be slowed or temporarily stopped. The subject will be monitored until symptoms resolve. If symptoms can be resolved with acetaminophen, diphenhydramine, or other medication (other than glucocorticoids) at the discretion of the investigator, the infusion may be restarted at the original rate, provided none of the criteria in Section 5.5.2 *Criteria for Permanent Discontinuation of Study Treatment* have occurred.

### 5.5.2 Criteria for Permanent Discontinuation of Study Treatment

Study treatment will be discontinued permanently for any individual subject under the following conditions:

1. At any time prior to or during the PolyTreg infusion at the request of the subject
2. If investigators or NIAID determine that the subject's health, safety, and/or well-being are threatened
3. If an infusion reaction symptom that caused a slow or temporary stop of the infusion cannot be resolved with acetaminophen or diphenhydramine
4. If administration of glucocorticoids to treat an infusion reaction is required
5. If a subject experiences any of the following:
  - a. NCI-CTCAE Grade 3 or higher infusion-related reaction
  - b. NCI-CTCAE Grade 3 or higher cytokine release syndrome
  - c. Any other infusion related SAE

Subjects who discontinue protocol-specified treatment will be treated as medically indicated according to physician discretion. Refer to Section 5.5.3.1, *Procedures for Subject Withdrawal from the Study*.

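### When acetaminophen and diphenhydramine fail but another non-glucocorticoid drug resolves an infusion reaction, Section 5.3.2 read alone permits restart, while Section 5.5.2 item 3 requires permanent discontinuation

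*Combined protocol and SAP*

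**What the plan says.** Four sections of the combined protocol and SAP govern a reaction during the infusion.

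- **Section 5.3.2** (Administration): the infusion is slowed or paused. If symptoms resolve with acetaminophen, diphenhydramine, "or other medication (other than glucocorticoids) at the discretion of the investigator, the infusion may be restarted at the original rate". No condition follows, but the paragraph ends with a pointer to Section 5.5.1, "Criteria for Interruption of Study Treatment".
- **Section 5.5.1**: the same rule, with the same three routes ("If symptoms can be resolved with acetaminophen, diphenhydramine, or other medication (other than glucocorticoids) at the discretion of the investigator"). It adds that restart is allowed "provided none of the criteria in Section 5.5.2" have occurred.
- **Section 5.5.2**: a mandatory list of grounds for permanent discontinuation. Item 3 is a reaction symptom that slowed or paused the infusion and "cannot be resolved with acetaminophen or diphenhydramine". Item 4, separately, is a need for glucocorticoids.
- **Section 5.6**: refers the reader to 5.5.2 for when to slow, pause or permanently stop the infusion.

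Two further places bear on the point. Section 5.6.2 says that Section 5.3.1 describes the drugs that may be used to treat infusion reactions, and 5.3.1 includes an NSAID course that "may be prescribed if the patient exhibits a fever not relieved by acetaminophen". On duration, Section 5.1.1 has the product "administered via IV over a 10-30 minute period by gravity", while Section 5.3.2 has it given "via gravity in approximately 20 to 30 minutes".

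**The concern.** Sections 5.3.2 and 5.5.1 both name a third, non-glucocorticoid drug as a route to restart. Item 3 of 5.5.2 leaves that route out and makes failure of the two named drugs a ground for permanent discontinuation. Either the repeated phrase or the omission looks like a drafting slip, and the text does not show which was intended.

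The rule is applied at the bedside, during an infusion of half an hour or less, at about four sites (Section 3.1). Section 1.3.1.3 describes the trial as the first experience of the technique in pemphigus patients. The outcome also decides whether a subject receives the whole cell dose or part of it. Dose escalation is first reviewed on four cohort 1 subjects, so one subject handled differently under two readings is a visible share of that evidence.

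**Working it through.** The plan gives no figure on this point, so the check is mainly a comparison of text. The table takes each way a reaction can end and reads off the three operative sections, assuming that no other criterion in 5.5.2 applies.

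| Course of the reaction | 5.3.2 read alone | 5.5.1 with its proviso | 5.5.2 | Agree? |
|---|---|---|---|---|
| Resolves with acetaminophen or diphenhydramine | may restart | may restart | no item met | yes |
| Glucocorticoid needed | no restart route | no restart route | item 4: permanent stop | yes |
| No drug resolves it | no restart route | no restart route | item 3: permanent stop | yes |
| Third non-glucocorticoid drug given first or alongside; resolves | may restart | may restart | item 3 not shown to be met | no clear conflict |
| Both named drugs fail; third non-glucocorticoid drug resolves | may restart | route named, then cancelled by the proviso | item 3: permanent stop | **no** |

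Only the last row conflicts. In that row 5.5.1 sides with 5.5.2, because item 3 has been met and the proviso blocks restart. The defect in 5.5.1 is that its third-drug route has no effect once both named drugs have failed.

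**Section 5.6.** Its reference to 5.5.2 promises criteria for slowing and pausing. Section 5.5.2 contains only grounds for permanent discontinuation; slowing and pausing are described in 5.3.2 and 5.5.1.

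**Is the conflicting row foreseeable?** Section 5.3.1 gives both named drugs about 30 minutes before the infusion and allows repeats every six hours as needed. With an infusion of at most 30 minutes, a reaction during it begins within about 30 + 30 = 60 minutes of premedication. Such reactions would therefore ordinarily arise with both drugs already given. Sections 5.3.1 and 5.6.2 together also foresee an NSAID.

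**Size.**
- At most 12 subjects are infused (Section 3.1).
- The only proxy is the T1DM study: four subjects had one event each within 24 hours of infusion, all mild (Section 1.5.2.3), among 14 treated (Section 1.3.2.1.1). That is 4/14 = 29% with any such event. The documents do not say whether any of those infusions was paused or a third drug used.
- One subject among the four in the first escalation review is 1/4 = 25%.
- The lower dose limit in Table 3.1 is 70% of target in both cohorts (0.7/1.0 and 1.75/2.5). For a bag holding exactly the target dose, stopping before 70% of the cells have been given leaves the subject below that limit.

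**Duration.** For the 100 ml volume in Table 3.1, average rate = volume / time:
- 100/10 = 10 ml/min at the lower limit in Section 5.1.1.
- 100/20 = 5 ml/min at the lower limit in Section 5.3.2.
- 100/30 = 3.3 ml/min at the shared upper limit.

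The range in 5.3.2 lies wholly inside the range in 5.1.1, and only the lower limits differ.

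**The case against.** The strongest reply is that the documents already say which section controls. The restart paragraph in 5.3.2 points to 5.5.1, 5.5.1 defers to 5.5.2, and 5.6 also names 5.5.2. A careful reader arrives at item 3. Restart is also permissive, so 5.3.2 compels nobody to resume.

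Much of this stands, and it rules out several stronger readings that a reader might infer:

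- *That 5.5.1 also leads to restart.* It does not; its proviso makes item 3 govern.
- *That staff reading 5.3.2 would restart.* The text says that they may, and it carries a cross-reference.
- *That any use of a third drug triggers the conflict.* Item 3 requires that the two named drugs could not resolve the symptom.
- *That the NSAID sentence is itself a restart rule.* Section 5.3.1 speaks of a course for fever and says nothing about resuming an infusion. It shows only that a third drug is foreseen.
- *That the two durations make the restart rate ambiguous.* The original rate naturally means that subject's own rate before slowing.
- *That the dose received would go unrecorded.* Nothing in the documents shows this. Section 7.5.2 mentions study drug administration pages, and Section 5.5.2.1 keeps subjects with an abbreviated infusion in follow-up where possible.

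What the reply does not remove is that 5.3.2, the section used to give the infusion, states the permission without the condition. The chain of references also ends by cancelling a route that two sections write out. The pointer in 5.6 does not repair this, since its target does not contain all that it promises.

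**Conclusion.** The inconsistency is real and narrow. For one case, failure of both named drugs followed by success of another non-glucocorticoid drug, 5.3.2 read alone permits restart and 5.5.2 item 3 requires permanent discontinuation. Section 5.5.1 does not add a second conflicting permission; it contains a route that has no effect in this case.

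The number of subjects affected cannot be computed, because the documents give no rate of paused infusions or of third-drug use. With at most 12 infusions and only mild events in the proxy study, it is probably small. The point merits correction because it concerns an operative stopping rule and is cheap to settle, not because many subjects are expected to meet it. The duration mismatch is minor.

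The conclusion assumes that item 3 means what it lists, namely the two named drugs and no others. If the sponsor intended those two as examples, the wording still needs to say so.

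**What to change.** The sponsor should reconcile Sections 5.3.2, 5.5.1, 5.5.2 item 3 and 5.6 so that a reaction unresolved by acetaminophen and diphenhydramine, but resolved by another non-glucocorticoid drug, has one outcome wherever the rule appears. Which outcome is a clinical decision on which this review takes no position. Whichever is chosen:

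- Section 5.3.2 should carry the same condition as 5.5.1, or give the reference in place of a restated rule.
- Sections 5.5.1 and 5.5.2 item 3 should use the same list of drugs, or say plainly why they differ.
- Section 5.6 should point to the sections that cover slowing and pausing as well as to 5.5.2.

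At the same time, the infusion duration should be stated once, or identically, in Sections 5.1.1 and 5.3.2.

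The cost is wording in four sections for the stopping rule and, for the duration, possibly a fifth (5.1.1). No procedure, visit or analysis is added.
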